8.3.3. Follow-up of AEs and SAEs

After the initial AE/SAE report, the Investigator is required to proactively follow each participant at subsequent visits/contacts. All SAEs will be followed until resolution, stabilization, the event is otherwise explained, the participant is lost to follow-up, or until the condition becomes chronic in nature (as defined in [Section 7.3](#)). Further information on follow-up procedures is provided in [Appendix C](#).

8.3.4. Regulatory Reporting Requirements for SAEs

- Prompt notification by the Investigator to the Sponsor of an SAE is essential so that legal obligations and ethical responsibilities towards the safety of participants and the safety of a study intervention under clinical investigation are met.

- The Sponsor has a legal responsibility to notify both the local regulatory authority and other regulatory agencies about the safety of a study intervention under clinical investigation. The Sponsor will comply with country-specific regulatory requirements relating to safety reporting to the regulatory authority, Institutional Review Boards (IRB)/Independent Ethics Committees (IEC), and Investigators.
- An Investigator who receives an Investigator safety report describing an SAE or other specific safety information (e.g., summary or listing of SAEs) from the Sponsor will review Investigator Site Files and notify the IRB/IEC, if appropriate, according to local requirements.
- Investigator safety reports must be prepared for suspected unexpected serious adverse reactions according to local regulatory requirements and Sponsor policy and forwarded to Investigators as necessary. Expedited reporting within 7 days will be made for events deemed life threatening or death. For all other serious events, reporting shall occur within 15 days.

8.3.5. Pregnancy

- Details of all pregnancies in female partners of male participants will be collected after the start of study intervention and until the time period for reporting pregnancies aligns with the time period for post-intervention contraception determined in [Section 5.1](#).
- If a pregnancy is reported, the Investigator will record pregnancy information on the appropriate form and submit it to the Sponsor within 24 hours of learning of the pregnancy of the female partner of the participant (after obtaining the necessary signed informed consent from the female partner).
- While pregnancy itself is not considered to be an AE or SAE, any pregnancy complication or elective termination of a pregnancy for medical reasons will be reported as an AE or SAE.
- Abnormal pregnancy outcomes (e.g., spontaneous abortion, fetal death, stillbirth, congenital anomalies, ectopic pregnancy) are considered SAEs and will be reported as such.
- The pregnant female partner of the participant will be followed to determine the outcome of the pregnancy. The Investigator will collect follow-up information on the pregnant female partner and the neonate, and the information will be forwarded to the Sponsor.
- Any post-study pregnancy-related SAE considered reasonably related to the study intervention by the Investigator will be reported to the Sponsor as described in [Section 8.3.4](#). While the Investigator is not obligated to actively seek this information in former study participants' pregnant female partner, he or she may learn of an SAE through spontaneous reporting.

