	Open-label Treatment Period											CSP Section Appendix
	20	21	22	23	24	25	26	27	F/U ^g	ET 3m ⁱ	ET 6m ⁱ	
Visit Identifier	20	21	22	23	24	25	26	27	F/U ^g	ET 3m ⁱ	ET 6m ⁱ	
Study Month ^h	13.5	15	16.5	18	19.5	21	22.5	24/ET ^b	25			
Visit Window (Days)	±5	±5	±5	±5	±5	±5	±5	±5	±5	±7	±7	
Site visit		X		X		X		X		X	X	NA
Telemedicine video call	X		X		X		X		X			NA
Physical and neuro exam		X		X		X		X				8.2.1
Weight								X				NA
Height								X				NA
Vital signs		X		X		X		X				8.2.2
Hematology/Chemistry ^d		X		X		X		X				8.2.3
Coagulation ^d								X				8.2.3
PK sampling		X		X		X		X		X		8.4
Biomarker collection		X		X		X		X		X	X	8.6
SomaScan [®] collection		X		X		X		X		X	X	NA
Dispensing		X		X		X						NA
Dose administration	→	→	→	→	→	→	→					6.1.1
Accountability		X		X		X		X				6.2
NSAA and NSAD		X		X		X		X				8.1.1.1
4-stair climb, 100-m timed test		X		X		X		X				8.1.1.2, 8.1.1.3
Muscle strength and Hand grip		X		X		X		X				8.1.1.4
DXA assessment								X				8.2.6
Cardiac assessment - Echo								X				8.2.5
Spirometry				X				X				8.2.7
12-lead electrocardiogram				X				X				8.2.4
C-SSRS				X				X				8.2.9
ACTIVLIM, PROMIS-57		X		X		X		X				8.1.2.1, 8.1.2.2
Contraception check	→	→	→	→	→	→	→	→	→			NA
Concomitant medications	→	→	→	→	→	→	→	→	→			6.8
SAE and AE monitoring	→	→	→	→	→	→	→	→	→			8.3

AE = adverse event; ACTIVLIM = measure of activity limitations for patients with upper and/or lower limb impairments; CSP = clinical study protocol; C-SSRS = Columbia Suicide Severity Rating Scale; D = Day; DXA = dual-energy X-ray absorptiometry; ET = early termination; m = meter; NA = not applicable; NSAA = North Star Ambulatory Assessment; NSAD = North Star Assessment for Limb Girdle Type Muscular Dystrophies; PK = pharmacokinetics; PROMIS-57 = Patient-Reported Outcomes Measurement Information System – 57 items; SAE = serious adverse event; “X” = in-clinic; “→”=continuously
Screening assessments may be performed over 2 days.

- a Day 2 Site visit for **Treatment-naïve participants only**
- b Early termination laboratory tests and assessments should mimic those of Month 24 however Medical Monitor discretion may be utilized especially if assessments were recently completed. Participants who withdraw prior to the Month 24 visit for non-safety reasons may re-enroll under the current protocol, or based on availability, the planned open-label extension study.
- c For treatment-naïve participants vital signs should be assessed 1, 2, 4, and 6 hours post-dose on Day 1

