- d All laboratory tests must be performed before functional assessments
- e Serology only collected for participants enrolling from outside EDG-5506-001
- f Single PK to be collected at each visit, except for Day 1. For treatment-naïve participants Day 1 is a serial collection at pre-dose, 0.25, 0.5, 1, 1.5, 2, 3, 4, 6, and 24 hours post-dose. The last timepoint is on Day 2. The dose on Day 2 should be administered only after the 24 hour timepoint. For treatment experienced, Day 1 is pre-dose only.
- g Based on availability, participants may roll over to the planned open-label extension prior to the Month 24 visit after completion of the ET visit. They are not required to perform the safety follow-up.
- h Starting at visit 10, study months are defined as 30 days. Monthly visits will be separated by 30 days +/- the visit window.
- i Laboratory collections for participants who withdraw prior to the Month 24 visit.

2. Introduction

EDG-5506, a first-in-class orally bioavailable, small molecule that selectively inhibits type II fast skeletal muscle myosin is being developed for the treatment of Becker muscular dystrophy (BMD).

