5.1. Inclusion Criteria

Participants are eligible to be included in the study only if all the following criteria apply:

1. Type of Participant and Disease Characteristics

Participants who have completed Study EDG-5506-001.

Participants who were not from Study EDG-5506-001 must meet the following:

- a. Male sex at birth and aged 18 to 55 years inclusive at time of consent.
- b. Documented dystrophin mutation with phenotype consistent with BMD.
- c. Ambulatory at Screening (defined as ability to complete 100 meter [m] timed test, with or without assistance).
- d. Body weight \geq 50 kg at the Screening visit.
- e. Body mass index (BMI) between 20 and 34 kg/m² inclusive.

2. Sex and Contraceptive/Barrier Requirements

Female sexual partners of male participants must use highly effective contraception (<1% failure rate per year) through 6 months after last dose.

- f. Participants must agree to not donate sperm during the study and for at least 6 months after last dose.

3. Informed Consent

Capable of giving signed informed consent as described in [Appendix A](#), which includes compliance with the requirements and restrictions listed in the informed consent form (ICF) and in this protocol.

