7.2. Participant Discontinuation/Withdrawal from the Study

- A participant may withdraw from the study at any time at his/her own request or may be withdrawn at any time at the discretion of the Investigator for safety, behavioral, or compliance reasons. This is expected to be uncommon.
- At the time of study discontinuation, if possible, an early discontinuation visit should be conducted, as shown in the SoA ([Table 1](#)). See the SoA for data to be collected at the time of study discontinuation and follow-up and for any further evaluations that need to be completed.
- The participant will be permanently discontinued both from the study intervention and from the study at that time. However, participants who withdraw for non-safety reasons may re-enroll (e.g., for family planning due to contraceptive requirement within the study)

and may return at a later date (e.g., once able to comply with contraceptive requirements again).

- If the participant withdraws consent for disclosure of future information, the Sponsor may retain and continue to use any data collected before such a withdrawal of consent.
- If a participant withdraws from the study, he/she may request destruction of any samples taken and not tested, and the Investigator must document this in the site study records.

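### Table 1 schedules no contraception check at the ET 3m and ET 6m site visits, although partner contraception and pregnancy collection run to 6 months after last dose

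*Protocol*

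**What the plan says.** **Requirement.** Protocol Section 5.1 says female partners "must use highly effective contraception (<1% failure rate per year) through 6 months after last dose". It also bars sperm donation for at least 6 months.

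**Pregnancy collection.** Protocol Section 8.3.5 has details of all partner pregnancies collected from the start of study drug "until the time period for reporting pregnancies aligns with the time period for post-intervention contraception", and refers to Section 5.1 for that period. The site must submit a pregnancy form within 24 hours of learning of a pregnancy, and must follow the pregnancy to its outcome.

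**Withdrawal.** Protocol Section 7.2 says that "participants who withdraw for non-safety reasons may re-enroll (e.g., for family planning due to contraceptive requirement within the study") and can come back later.

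**Schedule.** In the second part of Table 1 (Protocol Section 1.3), the row "Contraception check" carries arrows from Visit 20 through the Month 25 follow-up call and is empty under ET 3m and ET 6m. Both of those columns are marked as site visits. Footnote i gives their purpose: "Laboratory collections for participants who withdraw prior to the Month 24 visit". The rows for concomitant medications and for SAE and AE monitoring are empty there as well. Footnote b covers the early-termination visit itself: "Early termination laboratory tests and assessments should mimic those of Month 24", and the Month 24/ET column does carry the contraception check.

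**The concern.** The period over which the protocol wants to know about partner pregnancies is longer than the period over which anyone is scheduled to ask. The follow-up duties in Section 8.3.5 (the form, the pregnancy outcome, information on the newborn) cannot start until the site learns of a pregnancy. For early withdrawals, Table 1 already brings the participant to the site twice after leaving, but the schedule for those visits lists only sample collection.

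The group matters. Section 7.2 anticipates that some participants may leave because of the contraceptive requirement. Good adherence cannot be taken for granted in men who leave for that reason, and some of them could be trying to conceive inside the 6-month window. What is at stake is knowledge of possible fetal exposure to a first-in-class drug. No efficacy, safety or PK summary is at risk.

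**Working it through.** The plan gives no figure to reproduce. The check is a reading of Table 1 against the text, with a little arithmetic on timing.

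**1. Where the blanks fall.** The second part of Table 1 has 11 visit columns: Visits 20 to 27 (8), F/U (1), ET 3m (1) and ET 6m (1). The contraception row has 9 arrows followed by 2 empty cells, and 9 + 2 = 11, so the empty cells are ET 3m and ET 6m. Neighbouring rows confirm the alignment:
- Site visit, biomarker and SomaScan collection are marked at both ET columns.
- PK sampling is marked at ET 3m only.
- Dose administration has 7 arrows (Visits 20 to 26) and 4 blanks.

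No other section of either document schedules a contraception or pregnancy check after the follow-up call.

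**2. Whether the other blank rows explain this one.** The end of collection differs by data type:
- AEs and SAEs: Protocol Section 8.3.1 ends collection at the follow-up visit. Empty AE/SAE cells at ET 3m and ET 6m agree with that rule.
- Partner pregnancies: Section 8.3.5 ties collection to the Section 5.1 period, which is 6 months after last dose. Empty cells at ET 3m and ET 6m leave that period without a scheduled question.

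**3. Whether the protocol excuses the site from asking.** Section 8.3.1 frees investigators from actively seeking AEs or SAEs once participation has ended. Section 8.3.5 has a similar clause for post-study pregnancy-related SAEs. The same section says that pregnancy itself is neither an AE nor an SAE, so neither clause reaches the occurrence of a pregnancy.

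**4. Timing.** Footnote h says: "Starting at visit 10, study months are defined as 30 days". Applied to the contraception window, 6 × 30 = 180 days. Three assumptions are needed, none of them stated: that the early-termination visit coincides with last dose, that ET 3m and ET 6m are counted from it, and that the 30-day month applies to them. Then:
- ET 3m, with its ±7-day window: 90 ± 7 = days 83 to 97.
- ET 6m: 180 ± 7 = days 173 to 187.
- The last scheduled check is at the early-termination visit (day 0) or, if a follow-up call is made one month later, at about day 30.

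Most of the 180 days then has no scheduled check, although one site visit falls near the middle of the window and another at about its end.

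**The case against.** **The ET visits are for laboratory samples only.** Footnote i says so, and Section 7.2 treats a withdrawing participant as discontinued from the study. Several rows stop together, so the blanks may well be deliberate. This stands as an account of how they arose. A reader might infer that the contraception row was singled out or overlooked, and the documents do not support that. The explanation fits AE and SAE monitoring, which ends at follow-up by rule. It does not fit pregnancy collection, which continues.

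**The duties hold without a mark in the table.** Section 5.1 binds the participant, and Section 8.3.5 obliges the site to report a pregnancy it learns of. This stands too. A reader might infer that the protocol contradicts itself or has no provision for these pregnancies, and neither is true. What is missing is a scheduled occasion for learning of one.

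**Ascertainment may be arranged elsewhere.** The consent form is not in the public copy and may ask participants to report a partner's pregnancy themselves. That cannot be checked. It would reduce the gap, but it would not be a reason to leave out the question at a visit already taking place.

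**The timing is uncertain.** Section 7.1 lets a participant stop drug and remain in the study, and scheduled checks would then continue after last dose. Table 1 also defines the arrows as continuous activity rather than dated checks. Both points count against putting a firm percentage on the uncovered time, and none is given here. The arrows still end at the follow-up call.

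**Family planning is only an example.** Section 7.2 offers it as an illustration and expects withdrawal to be uncommon. No document says that anyone left for that reason.

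**Conclusion.** The point holds as a gap in ascertainment for participants who withdraw before Month 24. The site is scheduled to see them at ET 3m and ET 6m, within or at about the end of the period in which partner contraception is required and partner pregnancies are to be collected, but is not scheduled to ask about either.

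Its size can be given only conditionally: if the early-termination visit coincides with last dose and the ET visits count from it, most of the 6-month window has no scheduled check. A reader might want an expected number of missed pregnancies. The documents give no basis for one in this group, because the failure rate of under 1% per year in Section 5.1 describes partners who are using contraception, not people who may have left in order to conceive.

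The conclusion also rests on reading the awkward sentence in Section 8.3.5 as the 6 months of Section 5.1, which is the only post-intervention contraception period that the protocol states. No endpoint, analysis set or summary changes, and the SAP lists no output based on contraception or pregnancy data. The length of the 6-month period is not in question.

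**What to change.** In Table 1, mark the contraception check at ET 3m and ET 6m and attach a partner-pregnancy question to it. The question has to be written in explicitly, because the row's section reference is NA and the protocol does not define what the check covers. Extend footnote i so that these visits are no longer described as laboratory collections alone.

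The cost is two marks in the table and one added question at each of two visits that already take place. No visit is added and the end-of-study definition in Section 4.4 is unaffected.

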8.4. Pharmacokinetics

Samples will be collected for measurement of concentrations of EDG-5506 and metabolites of EDG-5506 as specified in the SoA ([Table 1](#)).

8.5. Genetics and/or Pharmacogenomics

Genetics are not evaluated in this study.

8.6. Biomarkers

- Samples for biomarker research will be collected from all participants in this study as specified in the SoA.
- Biomarker samples will be used for analysis of fast and slow skeletal troponin I, cardiac troponin I, cardiac troponin T, NT-proBNP, myoglobin, and creatine kinase.
- In addition, these biomarker samples will be stored and used for biomarker research related to pathophysiology of muscular dystrophies.
- No samples for genetic, genomic, or RNA analysis will be taken.
- SomaScan® proteomics analysis will be performed to identify potential biomarkers and include evaluation of association under exploratory endpoints.

8.7. Immunogenicity Assessments

Not applicable.

8.8. Medical Resource Utilization and Health Economics

Medical resource utilization and health economics parameters are not evaluated in this study.

9. Statistical Considerations

9.1. Statistical Hypotheses

No hypothesis testing is planned for this study.

9.2. Sample Size Determination

Sample size has been set empirically based on the number of participants who completed (through Day 42) the first-in-human study, EDG-5506-001. If necessary, additional (treatment-naïve) participants from outside the EDG-5506-001 study may be enrolled to meet the target enrollment of approximately 8 evaluable participants to provide reasonable estimates of PK and important safety/tolerability for this early stage of clinical development. No formal statistical hypothesis testing is planned. An evaluable participant is defined as a participant who completes the open-label treatment period without significant protocol deviations.

9.3. Analysis Sets

The analysis populations are described in [Table 4](#).

Table 4 Analysis Sets

Participant Analysis Set	Description
Safety Population	All participants who received at least one dose of study intervention
PK Evaluable Population	All participants who received at least one dose of study intervention and have a sufficient PK profile to derive at least one PK parameter

PK = pharmacokinetics.

Additional populations may be defined in the statistical analysis plan (SAP).

9.4. Statistical Analyses

The SAP will be finalized prior to database lock, and it will include a more technical and detailed description of the statistical analyses described in this section. This section is a summary of the planned statistical analyses of the most important endpoints including primary and key secondary endpoints.

9.4.1. General Considerations

Continuous variables will be summarized using the number of observations, mean, standard deviation, median, minimum, and maximum. Categorical variables will be summarized using frequency counts and percentages.

9.4.2. Safety Analyses

All safety analyses will be made on the Safety Population. Safety data will be summarized in tables and listings.

Adverse events will be coded using the Medical Dictionary for Regulatory Activities (MedDRA). Incidence rates for treatment-emergent adverse events (TEAEs), will be summarized

overall, by maximum severity, and by relationship to EDG-5506. Serious adverse events will also be summarized.

The change from baseline in the following safety endpoints will be summarized at each scheduled assessment time point using descriptive statistics:

- Safety laboratory parameters
- Vital signs
- Physical and neurological examination
- ECG parameters
- LVEF as assessed by cardiac echogram
- Pulmonary function as assessed by FEV₁, FVC
- C-SSRS

9.4.3. Efficacy Endpoints

The change from baseline in the following efficacy endpoints will be summarized at each scheduled assessment time point using descriptive statistics:

- NSAA
- NSAD
- 4-stair climb
- 100-meter timed test
- Muscle strength testing

9.4.4. Clinical Outcome Endpoints

The change from baseline in the following efficacy endpoints will be summarized at each scheduled assessment time point using descriptive statistics:

- ACTIVLIM
- PROMIS-57

9.4.5. Biomarkers

The change from baseline in the following efficacy endpoints will be summarized at each scheduled assessment time point using descriptive statistics:

- Serum CK
- Serum cardiac troponin I
- Serum myoglobin
- Serum cardiac troponin T
- Serum NT-proBNP

- Plasma troponin I tissue-specific isoforms (fast skeletal, slow skeletal)
- Plasma SomaScan® proteomics

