2.2. Background

2.2.1. Disease Background

BMD is an inherited condition that causes progressive weakness and wasting of the skeletal and cardiac muscles. Structural impairment of muscle from the genetic truncation of the dystrophin protein leads to myofiber membrane stress, hypercontraction, and subsequent degeneration with muscle use. Biomarkers of myofiber degeneration can be assessed *in vivo* with an elevation of creatine kinase (CK) and troponin in the blood. Human skeletal muscle consists of both fast (type IIa, IIx) and slow (type I) myofibers defined by myosin isoform, a protein integral for muscle contraction. In muscular dystrophy, fast (type II) myofibers appear to be particularly susceptible to early myofiber degeneration that ultimately proceeds to irreversible loss of muscle function with severe disability and early death ([Webster 1988](#)). Preventing hypercontraction of fast myofibers and therefore circumventing the loss of dystrophin's structural function may prevent myofiber degeneration and preserve skeletal muscle function in BMD.

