2.3.3. Overall Benefit: Risk Conclusion

Considering the measures taken to minimize risk to participants in this study, the potential risks identified in association with EDG-5506 are justified by the anticipated benefits that may be afforded to participants with BMD.

3. Objectives and Endpoints

The study objectives and endpoints are summarized in [Table 2](#).

Table 2 Objectives and Endpoints

Objectives	Endpoints
Primary	

 To assess the safety and tolerability of EDG-5506 in adults with BMD 	
 Incidence, frequency, and severity of AEs and SAEs in those treated with EDG-5506
Secondary	

 To assess the change in individual safety parameters 	
 Incidence of treatment-emergent abnormal laboratory test results (clinical chemistry, hematology, coagulation, and urinalysis) Change from baseline in: 
 Safety laboratory parameters Vital signs Physical and neurological examination ECG parameters Cardiac function as assessed by an echocardiogram Pulmonary function as assessed by FEV₁, FVC C-SSRS

 To assess the PK of EDG-5506 in adults with BMD 	
 PK of EDG-5506
Tertiary/Exploratory	

 To investigate the effect of EDG-5506 on biomarkers of muscle fiber damage in adults with BMD 	
 Change from baseline in: 
 Serum creatine kinase Serum myoglobin Serum cardiac troponin I Plasma troponin I tissue-specific isoforms (fast skeletal, slow skeletal) Serum cardiac troponin T Serum NT-proBNP Plasma SomaScan® proteomics

 To assess the effect of EDG-5506 on functional measures in adults with BMD 	
 Change from baseline in: 
 NSAA NSAD 4-stair climb 100-meter timed test

 To assess the effect of EDG-5506 treatment on self-reported outcomes in adults with BMD 	
 Change from baseline in: 
 PROMIS-57 ACTIVLIM

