### 3.1.5 Summary Statistics

Categorical data will generally be summarized with counts and percentages of patients. The denominator used for the percentage calculation will be clearly defined. Continuous data will generally be summarized with descriptive statistics including n (number of non-missing values), mean, median, standard deviation, minimum, and maximum.

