### 3.2.2 *PK-Evaluable Population (PKP)*

The PK-evaluable population (PKP) includes all participants who received at least one dose of EDG-5506 and have a sufficient PK profile to derive at least one PK parameter. The PKP will be used for all summaries of PK and biomarker data.

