## 3.7 Biomarkers

Biomarker samples will be used for analysis of fast and slow skeletal troponin I, cardiac troponin I, cardiac troponin T, NT-proBNP, myoglobin and CK. Summary statistics of these values and associated listings will be provided.

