## APPENDIX A: TABLES, LISTINGS AND FIGURES

Table Number	Title	Population
	Subject Data and Study Conduct	
14.1.1	Participant Disposition	SAF
14.1.2	Demographics and Baseline Characteristics	SAF
14.1.3	Medical History	SAF
14.1.4	Concomitant Medications	SAF
14.1.5	Participant Exposure and Treatment Compliance	SAF
	Efficacy and Clinical Outcome Assessments	
14.2.1	NSAA	SAF
14.2.2	NSAD	SAF
14.2.3	Four-Stair Climb	SAF
14.2.4	100-meter Timed Test	SAF
14.2.5	10-m Walk/Run Test	SAF
14.2.6	Rise-From-Supine Test	SAF
14.2.7	Muscle Strength Test	SAF
14.2.8	ACTIVLIM	SAF
14.2.9	PROMIS-57	SAF
	Safety Assessments	
14.3.1	Overview of Adverse Events	SAF
14.3.2.1	Adverse Events by SOC and PT	SAF
14.3.2.2	Adverse Events by Maximum Severity, SOC and PT	SAF
14.3.2.3	Study-drug Related Adverse Events by SOC and PT	SAF
14.3.2.4	Treatment-Emergent Adverse Events Leading to Study	SAF

	Drug Discontinuation by SOC and PT	
14.3.2.5	Adverse Events Leading to Death by SOC and PT	SAF
14.3.3	Summary of Vital Signs	SAF
14.3.4.1	Summary of Clinical Laboratory Assessments: Chemistry	SAF
14.3.4.2	Summary of Clinical Laboratory Assessments: Hematology	SAF
14.3.4.3	Summary of Clinical Laboratory Assessments: Coagulation	SAF
14.3.4.4	Summary of Clinical Laboratory Assessments: Urinalysis	SAF
14.3.5	Summary of ECGs	SAF
14.3.6	Summary of DXA Assessments	SAF
	Pharmacokinetics	
14.4.1.1	Summary of Pharmacokinetics (PK) Concentrations	PK
	Biomarkers	
14.4.2.1	Summary of Biomarkers	PK

Listing Number	Title
	Disposition
16.2.1.2	Protocol Deviations
	Participant Demographics and Characteristics
16.2.4.2	Medical History
16.2.4.3	Concomitant Medications
	Exposure
16.2.5	Study Drug Exposure and Compliance
	Adverse Events

16.2.7.1.1	Adverse Events
16.2.7.1.2	Serious Adverse Events
	Other Safety Assessments
16.2.8.1	Vital Signs
16.2.8.2.1	Clinical Laboratory Assessments: Chemistry
16.2.8.2.2	Clinical Laboratory Assessments: Hematology
16.2.8.2.3	Clinical Laboratory Assessments: Coagulation
16.2.8.2.4	Clinical Laboratory Assessments: Urinalysis
16.2.8.3	ECGs
16.2.8.4	DXA
16.2.8.5	Spirometry
16.2.8.6	Physical and Neurological Examination
16.2.8.8	Echocardiogram
	Pharmacokinetics (PK) and Biomarkers
16.2.9.1.1	PK Concentrations
16.2.9.2.1	Biomarkers

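### Cardiac troponin I, cardiac troponin T and NT-proBNP have no safety-table analysis, and their only summary table is run on the PK-evaluable population

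*Protocol*

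**What the plan says.** Table 2 of the protocol puts the three cardiac markers under an exploratory objective: "To investigate the effect of EDG-5506 on biomarkers of muscle fiber damage in adults with BMD". Protocol 9.4.5 lists them with CK, myoglobin and the skeletal troponin I isoforms: "The change from baseline in the following efficacy endpoints will be summarized at each scheduled assessment time point using descriptive statistics". The safety list in Protocol 9.4.2 has one imaging item for the heart, "LVEF as assessed by cardiac echogram", plus ECG parameters and vital signs, but no cardiac blood marker. The secondary endpoint on treatment-emergent laboratory abnormalities covers chemistry, hematology, coagulation and urinalysis. Appendix B puts the cardiac markers in a separate biomarker column.

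For biomarkers, SAP 3.7 states: "Summary statistics of these values and associated listings will be provided". SAP 3.1.5 defines the usual continuous summary as "descriptive statistics including n (number of non-missing values), mean, median, standard deviation, minimum, and maximum". SAP 3.2.2 sets the population: "The PKP will be used for all summaries of PK and biomarker data". In SAP Appendix A the only table is 14.4.2.1, "Summary of Biomarkers", with Listing 16.2.9.2.1 alongside. SAP 3.5.3, the safety laboratory section, names no cardiac troponin and no NT-proBNP.

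**The concern.** Safety and tolerability are the primary objective, and the protocol describes a disease that affects the heart: "BMD is an inherited condition that causes progressive weakness and wasting of the skeletal and cardiac muscles". Cardiac function is a secondary safety endpoint. In a trial of about 8 evaluable participants, cardiac safety is judged participant by participant: did anyone develop a new abnormal value, how high, when and on what dose? The plan answers that question for QTc (threshold counts, SAP 3.5.5) and partly for routine laboratory tests (normal and abnormal categories by visit, SAP 3.5.3), but not for the three cardiac blood markers.

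Echocardiography does not fill the gap, because SAP 3.5.8 presents it in listings only. The cardiac content of the 14.3 tables is therefore ECG, vital signs and any reported adverse events. A study report could draw a cardiac safety conclusion from its safety tables without using the cardiac measurement taken at the most visits.

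**Working it through.** There is no planned figure to reproduce: the sample size is empirical and no hypothesis test is planned. The check has four parts.

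**1. Scheduled post-baseline visits (Protocol Table 1, as it reads).**

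| Measurement | To Month 12 | After Month 12 | Total |
|---|---|---|---|
| Cardiac markers | Days 29, 57; Months 3, 4, 6, 7, 8, 10, 12 (9) | Months 15, 18, 21, 24 (4) | 13 |
| 12-lead ECG | Days 29, 57; Months 3, 4, 6, 8, 10, 12 (8) | Months 18, 24 (2) | 10 |
| Echocardiogram | Months 4, 12 (2) | Month 24 (1) | 3 |

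Marker visits with neither ECG nor echocardiogram: Months 7, 15 and 21, which is 3 of 13. Month 7 is Visit 14, the first site visit after the step to 20 mg at Visit 13. Month 15 is Visit 21, where 20 mg ends. Month 21 falls in the later 10 mg period. Vital signs are taken at all three visits, and a physical examination at Months 15 and 21, but neither is a cardiac-specific measurement.

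**2. Planned displays, side by side.**

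| Data | Table | Count of abnormal or outlying values | Population |
|---|---|---|---|
| Routine laboratory tests | 14.3.4.1 to 14.3.4.4 | Yes (SAP 3.5.3) | Safety |
| ECG | 14.3.5 | Yes (SAP 3.5.5) | Safety |
| Echocardiogram | None; Listing 16.2.8.8 | No | – |
| Cardiac markers | 14.4.2.1; Listing 16.2.9.2.1 | No | PK-evaluable |

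**3. What the planned statistics show of one participant's rise.** Suppose one participant's change from baseline is R and the others' is 0. With n = 8:
- mean change = R/8 = 0.125R
- median change = 0
- maximum change = R

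With n = 12 (an assumed upper range, since the enrolled number is not stated), the mean change is R/12 = 0.083R, and the median and maximum are unchanged. So the mean and median dilute the rise and the maximum shows it in full.

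That holds only if the change is tabulated. SAP 2.2 makes change from baseline the endpoint, but SAP 3.7 promises summaries of the values. On raw values, if one participant goes from a to a + R while another stays at b > a + R, the maximum is b at both visits and the rise does not appear in it. Even a maximum change gives no baseline, no dose at the peak and no number of participants affected.

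**4. Who is in the table.** SAP 3.2.2 requires a PK profile sufficient to derive at least one PK parameter. Under footnote f of Table 1, treatment-experienced participants give a single sample at each visit, pre-dose only on Day 1. Protocol 9.4.6 plans PK parameters only for treatment-naïve participants on Day 1. Protocol 2.2.2 reports 5 adults with BMD dosed with EDG-5506 in EDG-5506-001. If treatment-experienced means those 5 and all of them enrolled, a strict reading puts up to 5 participants outside the only marker table.

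**The case against.** The case on the other side is substantial. A reader might infer that only group statistics are planned and that an individual rise would disappear in them. The documents do not support that. SAP 3.7 promises listings, Listing 16.2.9.2.1 is planned, SAP 6 lists all available data by patient, and SAP 3.1.5 includes the maximum. With about 8 participants, a listing by visit can be read line by line.

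Nor are cardiac data thin across the board. ECG is scheduled at 10 post-baseline visits, in triplicate, with QTc threshold counts. The efficacy label is the protocol's and repeats the sentence used in 9.4.3 and 9.4.4; the SAP, which supersedes the protocol's statistical section, files the markers under biomarkers rather than efficacy. Protocol 2.2.1 names troponin as a marker of myofiber degeneration, which explains the grouping of the troponins, though not of NT-proBNP. Protocol 2.2.2 describes the drug as inactive against the slow myosin present in the heart, so nothing here implies that cardiac harm is expected.

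There is also a route into the safety tables. Appendix B includes the markers among the laboratory tests, and Protocol 8.2.3 requires clinically significant changes to be recorded as adverse events.

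All of this stands, but it does not close the gap. ECGs and routine laboratory values are also listed, and the SAP still tabulates them. The adverse event route depends on judgement: Protocol 8.2.3 and Appendix C set aside abnormalities attributed to the underlying disease unless more severe than expected, and in BMD a cardiac-marker rise can be so attributed. The documents do not say whether biomarker results reach the investigator in time for that review.

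**Conclusion.** The point holds as a gap in analysis and display. The three cardiac markers are in no 14.3 table, have no abnormality, shift or threshold count, and are summarised only on the PK-evaluable population. A rise can be found in a maximum, a listing or a reported adverse event, but no planned safety output counts or characterises it. The gap concerns 13 post-baseline visits per participant, at 3 of which no other cardiac-specific measurement is scheduled.

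The visit counts rest on Table 1 as it reads. The population point is conditional. It bites only if a single concentration per visit is held insufficient to derive a parameter. Protocol 9.4.6 plans exposure summaries for treatment-experienced participants, which suggests that dropping them is not intended, but the SAP wording permits it. The documents do not support concluding that participants will in fact be lost, or that a cardiac signal would go unseen.

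The change is worth making because safety is the primary objective and the data already exist.

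**What to change.** 1. In SAP 3.2.2 and 3.7, summarise cardiac troponin I, cardiac troponin T and NT-proBNP on the Safety Population, and state that both values and change from baseline are tabulated.
2. Under SAP 3.5, add one safety table with a row per participant and marker: baseline value, highest post-baseline value, their ratio, and the visit and dose at the peak. Add the number of participants newly above the assay ULN (not above it at baseline) or above a threshold the sponsor sets in advance. This is a reporting threshold and alters no treatment decision.
3. Leave the markers listed as exploratory biomarkers, so the objectives tables need no change. The plan already handles one analyte both ways: creatine kinase is a chemistry test in SAP 3.5.3 and a biomarker in SAP 3.7.

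The cost is SAP wording and one added table, with no new sample or procedure. The downside is small: with 13 post-baseline values per participant, individual maxima will include some chance excursions, and some elevations may reflect the underlying disease. A table footnote should say so.
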